7.0 CLINICAL ACTIVITY

Evidence of clinical activity will be assessed by the VAS OA knee pain scores recorded at pre-dose ($\leq 30 \text{ min}$) on Days 1 2, 3, 4, and on Days 5, 19, 35, 64, and 94.

The WOMAC instrument will we be used to evaluate the effectiveness of CGS-200-1 and CGS-200-5 in the management of signs and symptoms of OA of the knee in addition to just management of OA knee pain on Days 5, 19, 35, 64, and 94.

8.0 SAFETY ASSESSMENTS

8.1 ADVERSE EVENTS

8.1.1 Definitions

The AE monitoring period begins with the start of study drug administration on Day 1 and continues through Day 94.

ADVERSE EVENT EXPERIENCE (AE) – any unfavorable or unintended sign, symptom, or disease that is temporally associated with the use of an investigational drug but is not necessarily caused by the investigational drug. This includes worsening (e.g.; increase in frequency or severity) of pre-existing conditions.

SERIOUS ADVERSE EVENT (SAE) – an AE resulting in any of the following outcomes:

- Death
- Life-threatening (**immediate** risk of death)
- Inpatient hospitalization
- Prolongation of existing hospitalization
- Persistent or significant disability or incapacity
- Congenital anomaly/birth defect
- Medically important*

*Important medical events that may not result in death, be life-threatening, or require hospitalization may be considered SAEs when, based upon appropriate medical judgment, may jeopardize the subject and may require medical or surgical intervention to prevent one of the outcomes listed in this definition. Examples of such medical events include allergic bronchospasm requiring intensive treatment in an emergency room or at home, blood dyscrasias or convulsions that do not result in a subject's hospitalization, or the development of drug dependency or drug abuse.

UNEXPECTED ADVERSE EVENT – any adverse event, the specificity or severity of which is not consistent with the current Investigator Brochure (IB). Expected means that the event has previously been observed with the study drug and is identified and/or

described in the current IB. It does not mean that the event is expected with the underlying disease(s) or concomitant medications.

8.1.2 Reporting to the Sponsor

All AEs that are identified from the start of study drug administration and through Day 94 will be documented in the source documents and the AE eCRF. All data fields on the AE eCRF should be completed.

SAE must also be documented on the SAE Worksheet and sent to the sponsor/designee within 24 hours of site personnel becoming aware of an SAE. The SAE Worksheet should be completed as much as possible but should not be held until all information is available. Additional information, follow-up information, and corrections should be provided on subsequent SAE Worksheets that are clearly identified as follow-up (#1, #2, etc.) reports. SAE Worksheets should be sent by Email with Telephone Notification to the Drug Safety Department at:

Drug Safety personnel will be available to answer questions and assist site personnel in documenting SAEs and completing the SAE worksheet.

8.1.3 Investigator Evaluation of Adverse Events

The determination of seriousness, severity and causality must be made by the *physician investigator* who is qualified to review AE information, provide a medical evaluation of AEs, and classify AEs based upon medical judgment. The investigator will evaluate all AEs with respect to seriousness (criteria listed above), severity, and causality (relationship to study drug) according to the guidelines listed below.

Severity will be graded using the RCTC, v2.0. The RCTC is provided in Appendix B. In the event that an AE does not have a RCTC code, the following severity classifications will be used:

SEVERITY

Grade 1: Mild
Grade 2: Moderate
Grade 3: Severe
Grade 4: Life Threatening*
Causing no limitation of usual activities
Causing some limitation of usual activities
Causing inability to carry out usual activities
Potentially life threatening or disabling

* *Note* – a severity assessment of Life Threatening is not necessarily the same as Life Threatening as a "Serious" criteria. The latter means that the event is an immediate threat to life as opposed to a potential threat to life.

8.1.3.1 Assessment of Seriousness

Event seriousness will be determined according to the protocol definition of SAE in Section 8.1.1.

8.1.3.2 Assessment of Severity

Event *severity* will be assigned according to the RCTC, v2.0.

8.1.3.3 Assessment of Causality

The investigator is required to provide an assessment of causality or relationship of AEs to the study drug based on 1) temporal relationship of the event to the administration of study drug; 2) whether an alternative etiology has been identified; and 3) biological plausibility. The causality assessment categories that will be used for this study are described below.

Note: If a causality assessment is not provided, a possible relationship will be assumed for regulatory reporting purposes.

Causality assessments that are considered **Not Related** to study drug:

None: The event is related to an etiology other than the study drug (the alternative etiology must be documented in the subject's medical record).

Unlikely: A clinical event, including laboratory test abnormality, with a temporal relationship to drug administration which makes a causal relationship improbable, and in which other drugs, chemicals or underlying disease provide plausible explanations. The event is unlikely to be related to the study drug and likely to be related to factors other than study drug.

Causality assessments that are considered **Related** to study drug:

Possible: A clinical event, including laboratory test abnormality, with a reasonable time sequence to administrations of the drug, but which could also be explained by concurrent disease or other drugs or chemicals. Information on drug withdrawal may be lacking or unclear.

Probable: A clinical event, including laboratory test abnormality, with a reasonable time sequence to administration of the drug, unlikely to be attributed to concurrent disease or other drugs or chemicals, and which follows a clinically reasonable response on withdrawal (dechallenge). Rechallenge information is not required to fulfill this definition.

Definite: A clinical event, including laboratory test abnormality, occurring in a plausible time relationship to drug administration, and which cannot be explained by concurrent disease or other drugs or chemicals. The response to withdrawal of the drug (dechallenge) should be clinically plausible. The event must be definitive pharmacologically or phenomenologically, using a satisfactory rechallenge procedure if necessary.

Note – ICH guidelines (3/95) clarify "reasonable causal relationship" to mean, "that there are facts (evidence) or arguments to suggest a causal relationship."

8.1.4 Follow-up of Adverse Events

Adverse events will be captured from start of study drug treatment through Day 94. AEs are followed until final outcome is known or until the end of the study Day 94. AEs that are not resolved as of Day 94 are recorded on the AE eCRF as ongoing and in the outcome field as Not Recovered/Not Resolved.

SAEs that have not resolved by Day 94 are followed until final outcome is known. If it is not possible to obtain a final outcome for a SAE (e.g., the subject is lost to follow-up), the reason a final outcome could not be obtained will be documented by the investigator.

Pregnancy:

All reports of pregnancy, or partner pregnancy, occurring after treatment with study drug and up to Day 94 must be reported via the Pregnancy Report form to Safety as per Section 8.1.2. Pregnancy itself is not an AE or SAE. However, any events arising during the pregnancy will be assessed and reported accordingly as an AE or SAE. A spontaneous abortion is always considered to be an SAE and shall be reported on the SAE Worksheet. Furthermore, any SAE occurring as a result of a post-study pregnancy and considered reasonably related to the investigational product by the investigator will be reported to Safety. All reported pregnancy cases will be followed up until outcome.

8.1.5 Post Study SAEs

SAEs that occur after the Day 94 visit that are assessed by the investigator to be possibly, probably, or definitely related to study drug must be reported to Safety on a SAE Worksheet, as described in Section 8.1.2. Post study SAEs will not be documented on the AE eCRF.

8.1.6 Reporting to the Institutional Review Board/Independent Ethics Committee

All SAEs that are considered unexpected and related to the investigational drug will be reported by Vizuri Health Sciences/designee as 15-Day (Expedited) reports to the regulatory authority AND to all participating investigators. Each investigator must notify the IRB/IEC responsible for reviewing the study at their site of all 15-Day Reports. Expected and unrelated SAEs will be reported periodically.

8.2 LABORATORY TESTS

Clinical laboratory tests (Appendix A) will be performed at Screening to determine eligibility and on Days 5 and 94 as outlined in Section 6.0.

All female subjects who are biologically capable of having children will have a serum pregnancy test at screening and urine pregnancy test prior to dosing on Day 1. The results of the pregnancy tests must be confirmed to be negative before administration of study drug. FSH testing will be performed on postmenopausal women for up to 2 years after cessation of menses to confirm postmenopausal status.

9.0 DATA ANALYSIS METHODS

9.1 DETERMINATION OF SAMPLE SIZE

A sample size analysis has been performed and suggests that a sample size of 40 evaluable subjects per each of the three study arms will appropriately power this study.

9.2 RANDOMIZATION AND BLINDING

Treatment assignment for all subjects enrolled in this study will be double-blind; the subjects and all site personnel and CRO personnel (with the exception of the Medical Monitor providing safety oversight) involved in this study will not know the treatment given to any subject. Every effort should be made to maintain the study blind.

9.3 ANALYSIS SETS

The following three analysis sets will be defined for this study:

The intent-to-treat (ITT) set will be defined as all randomized subjects, whether or not they receive study drug.

The modified ITT (mITT) set will be defined as the subset of the ITT subjects that receive at least one dose of study medication and have at least one evaluable post-dosing efficacy endpoint. The mITT set will be defined based on randomized treatment rather than treatment actually received. All efficacy analyses will be carried out using the mITT set.

The safety (SAF) set will be based on the ITT subjects, but will be based on the treatment actually received rather than randomized treatment. All safety analyses will be carried out using the SAF set.

9.4 SUBJECT ACCOUNTABILITY

All subjects who meet the inclusion criteria for the study, sign the informed consent form, and are enrolled and exposed to the study medication will be accounted for in the analyses. Subjects who are deemed 'screen failures' will not be accounted for in the data presentation of response or safety.

9.5 STATISTICAL METHODS

9.5.1 Analysis of Demographic and Subject Characteristics

Subject demographic characteristics including age, gender, race, weight, and height will be summarized by treatment group. Subject baseline disease characteristics that are relevant to the evaluation of the treatment will be summarized by treatment group.

9.5.2 Treatment Administration/Compliance

The Investigators will be responsible for the storage, dispensing, inventory, and accountability of all clinical supplies. An accurate, timely record of the disposition of all clinical supplies must be maintained. Subjects may be withdrawn from the study by the Sponsor for non-compliance with the protocol.

9.5.3 Efficacy Analyses

Primary Efficacy Endpoint

The group mean LMS difference between each Active Treatment Arm and the Vehicle Arm for the WOMAC pain score at Day 35 will be tested for significance of difference at a significance value of $p \le 0.05$.

Secondary Efficacy Endpoints

The group mean LMS difference between each Active Treatment Arm and the Vehicle Arm for the WOMAC stiffness, function and total score at Day 35 will be tested for significance of difference at a significance value of p < 0.05

Also, the group mean reduction in OA knee pain score on a 100 mm VAS scale for each active treatment arm will be compared to the vehicle arm and tested for significance of difference at a significance value of p < 0.05

For dose-response estimation:

The group mean LMS difference between the 5% and the 1% Active Treatment Arms for the WOMAC pain, stiffness, function and total score at Day 35 will be tested for significance of difference at a significance value of $p \le 0.05$

Efficacy analyses will be carried out on the mITT set.

9.5.3.1 Clinical Response

Clinical response will be measured by reduction of WOMAC pain score. In order for a subject to be considered to have successfully obtained a clinical response, the following criteria must be met:

WOMAC pain score reduced to 50% or less of baseline at any of the stated assessment times.

The durability of clinical response up to Day 94 will be evaluated by a tabulation of clinical response at a Days 19, 35, 64, and the Day 94 visit by treatment group. Subjects who have successfully met the above criteria (reduction of a least 50% in NRS pain score) at the Day 5 visit and who remain at least at this reduction of pain score or lower at the Day 35 visit will be considered to have a durable clinical response. Subjects who at the Day 35 visit have less reduction in WOMAC in OAKP score than they did at the Day 5 assessment will be considered to have failed to achieve a durable clinical response.

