9.5.7 Interim Analyses

Interim analyses will be performed at Days 19, 35, and 64 per 9.5.3 and 9.5.3.1 above,

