1. INTRODUCTION

This statistical analysis plan (SAP) is based on the Protocol # VZU00025, titled “A Phase 2 Double-Blind Clinical Trial to Examine the Comparative Effects on Osteoarthritic Knee Pain of CGS-200-1 (1% Capsaicin Topical Liquid), CGS-200-5 (5% Capsaicin Topical Liquid), and CGS-200-0 (Vehicle, No Capsaicin).” See the study protocol for full details.

This document details the statistical methods planned to perform the final analyses of the study. This study will involve application of CGS-200-1 and CGS-200-5 (which has 1% and 5% capsaicin respectively) or of a Vehicle CGS-200-0 (which has no capsaicin in it). Study analysis will include comparison of the treatment effect on osteoarthritis (OA) knee pain as assessed by the Western Ontario and McMaster Universities Index of Osteoarthritis (WOMAC) score for OA signs and symptoms.

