6.3 Clinical Response

Clinical response will be measured by reduction of WOMAC pain score on the Study Knee. In order for a subject to be considered to have successfully obtained a clinical response, the following criteria must be met: WOMAC pain score on the Study Knee reduced to 50% or less of baseline at any of the stated assessment times.

A subject with a missing WOMAC pain score on the Study Knee at a visit will be considered to have failed to achieve a clinical response for that visit.

The durability of clinical response up to Day 94 will be evaluated by a tabulation of clinical response at Days 19, 35, 64, and the Day 94 visit by treatment group. Subjects who have successfully met the above criteria (reduction of a least 50% in WOMAC pain score) at the Day 5 visit and who remain at least at this reduction of pain score or lower at the Days 19, 35, 64, and the Day 94 visit will be considered to have a durable clinical response through Day 94. Subjects who at no more than one of the post Day 5 visits have less than 50% reduction in WOMAC pain score will be considered to have a durable response through the last day at which reduction in WOMAC pain score is at least 50%. Patients who have less than 50% WOMAC pain score reduction on two or more of the post Day 5 visits will be considered to have failed to achieve a durable clinical response.

Each subject's clinical response status (Responder vs. Non-responder) at each visit and the durability of clinical response up to Day 94 will be summarized for each treatment group. Percent change from baseline in WOMAC pain score on both knees will be listed at each visit.

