8. INTERIM ANALYSES

The scope of this document details the final analysis to be performed by CTI, and does not describe any interim analysis that may be performed.

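### Protocol 9.5.3.1 fails a Day 5 responder for any smaller reduction at Day 35; at the Day 35 and Day 64 interim looks this would mislabel roughly three or four in ten stable responders

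*Protocol*

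**What the plan says.** **Protocol 9.5.3.1.** A clinical response is "WOMAC pain score reduced to 50% or less of baseline at any of the stated assessment times". Two sentences then define durability.

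- The first counts as durable those subjects who met the criterion at Day 5 and "who remain at least at this reduction of pain score or lower at the Day 35 visit". Its parenthesis calls the criterion an NRS reduction, although the section's criterion is WOMAC pain.
- The second says that subjects who at Day 35 "have less reduction in WOMAC in OAKP score than they did at the Day 5 assessment will be considered to have failed".

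**Protocol 9.5.7.** "Interim analyses will be performed at Days 19, 35, and 64 per 9.5.3 and 9.5.3.1 above".

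**SAP 6.3.** The SAP's revision table records that the durability definition was changed. Durability now rests on a fixed 50% threshold over Days 19, 35, 64 and 94. One visit below 50% is forgiven, and failure is reserved for "Patients who have less than 50% WOMAC pain score reduction on two or more of the post Day 5 visits".

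**SAP scope.** Section 1 states: "This document details the statistical methods planned to perform the final analyses of the study". Section 8 adds that the SAP "does not describe any interim analysis that may be performed".

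**The concern.** The failure sentence compares two noisy 0–500 scores from the same person and treats any worsening as failure. Take a baseline of 300 for illustration. A subject at 60 on Day 5 (80% reduction) and 63 on Day 35 (79%) has failed. A subject at 150 and then 147 (50%, then 51%) is durable. If true pain has not changed, which score is higher is close to a coin toss. Choosing subjects because their Day 5 score was good tilts the toss against them, through regression to the mean.

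The two durability sentences also disagree if the first means a maintained 50% reduction. If instead it means holding the subject's own Day 5 reduction, the contradiction goes but both sentences then carry the no-tolerance rule.

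At stake is an interim description of durability. The protocol's background presents long-lasting relief after a short course as the unmet need, so this table will be read with interest. An understated interim figure would then sit beside a final table built on a different rule.

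**Working it through.** **1. Which analyses use the rule.**
- Final analysis: no. SAP 6.3 replaces it.
- Day 19 look: no. It cannot use a Day 35 comparison.
- Day 35 and Day 64 looks: yes. Protocol 9.5.7 points to 9.5.3.1, and SAP 1 and 8 do not reach interim analyses.

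**2. Check of the SD.** SAP 9 gives 80% power for a difference of 63 with SD 100 and 40 per arm. The standard error is 100 × √(2/40) = 22.36, and 63/22.36 = 2.817. Power is Φ(2.817 − 1.960) = Φ(0.857) = 80.4%. The plan's figure is reproduced. The documents give no figure for the durability rule itself.

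**3. Symmetry.** If Day 5 and Day 35 scores have the same distribution and nothing truly changes, then over all subjects

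P(Day 35 worse than Day 5) = (1 − P(tie)) / 2,

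whatever the SD. Without ties this is 50%.

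**4. Restriction to Day 5 responders, by simulation** (1,000,000 subjects per row).
- From the documents: SD of change 100 (SAP 9); score range 0–500 (SAP 9); entry floor 250 (Protocol 4.1.1).
- Mean reductions: 40% and 75% (U.S. and Dominican Republic vehicle, Protocol 1.1 and 1.3); 83% and 93% (vehicle and CGS-200-5 at 13 weeks in VZU00023, Protocol 1.3); 60% as an intermediate value. These are knee-pain figures from earlier studies and serve only to set a range.
- Assumed: baseline normal with mean 330 and SD 60, restricted to 250–500; Day 5/Day 35 correlation 0.5, 0.7 or 0.9; scores rounded to 1 mm; no true change between the visits.

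A Day 5 responder who is above half of baseline at Day 35 is necessarily worse than at Day 5. So

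total failed = (below 50% reduction at Day 35) + (still at 50% or more, but worse than Day 5).

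The first part fails under a plain 50% rule too. Only the second part is due to the quoted sentence.

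| Mean reduction | Correlation | Total failed | Also fails a 50% rule | Due to this sentence |
|---|---|---|---|---|
| 40% | 0.5 | 70.3% | 42.5% | 27.9% |
| 40% | 0.7 | 64.7% | 32.4% | 32.3% |
| 40% | 0.9 | 56.5% | 18.3% | 38.2% |
| 60% | 0.5 | 59.7% | 24.6% | 35.1% |
| 60% | 0.7 | 55.7% | 18.7% | 37.0% |
| 60% | 0.9 | 50.0% | 10.6% | 39.4% |
| 75% | 0.5 | 51.2% | 13.9% | 37.3% |
| 75% | 0.7 | 48.0% | 10.7% | 37.3% |
| 75% | 0.9 | 43.4% | 6.2% | 37.2% |
| 83% | 0.5 | 46.3% | 9.7% | 36.6% |
| 83% | 0.7 | 43.2% | 7.5% | 35.7% |
| 83% | 0.9 | 38.9% | 4.3% | 34.6% |
| 93% | 0.5 | 39.4% | 5.7% | 33.6% |
| 93% | 0.7 | 36.6% | 4.5% | 32.1% |
| 93% | 0.9 | 32.7% | 2.7% | 30.1% |

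Percentages are of Day 5 responders. Rows may miss adding up by 0.1 through rounding, and repeat runs differ by about half a point.

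**5. Behaviour near the floor.** At high mean reductions many scores are 0 at both visits, and a tie does not fail. At 93% and correlation 0.9, ties at 0 make up 36.6% of Day 5 responders. The model probably overstates such ties, because it keeps SD 100 next to the floor and a score of 0 needs all five items at 0.

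**The case against.** The strongest reply is that the result that counts has already been repaired. SAP 6.3 uses a 50% threshold, and the change is logged. Durability is in neither document's list of primary or secondary efficacy endpoints, no test is specified for it, and no stopping or adaptation decision hangs on an interim durability table. SAP 8 even speaks of interim analysis only as something that may happen. All of this stands and limits the point to two descriptive looks. It does not remove it: the protocol says the interims will be done per 9.5.3.1, and nothing extends SAP 6.3 to them.

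Three stronger readings are tempting.

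- **That the sentence itself wrongly fails half or more of stable responders.** The total reaches half or more at mean reductions of 40–60%, but 11–43% of Day 5 responders there would fail a plain 50% rule as well. At 83–93% even the total is only 33–46%.
- **That observed failures would be mainly noise.** The simulation sets true loss to zero, so it cannot divide real failures between noise and waning. In VZU00021 (Protocol 1.3) the share of knees meeting the 50% NRS criterion on CGS-200-05 went from 100% at Day 5 to 81% at Day 19 and 92% at Day 33, so some real movement cannot be excluded.
- **That a simple 50% rule judged at each visit would make interim and final tables agree.** SAP 6.3 forgives one lapse. A subject below 50% only at Day 35 fails the simple rule at that visit, yet is durable through Day 94 under the SAP.

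**Conclusion.** The rule is wrong as written, within narrow limits. It affects the Day 35 and Day 64 interim durability tabulations and nothing else.

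With no true loss of effect, the quoted sentence alone would label about 28–39% of Day 5 responders as failed for mean reductions of 40–75%, and about 30–37% for 83–93%, although they still hold a 50% reduction. Total failures would be about 57–70% at a 40% mean reduction, 50–60% at 60%, 43–51% at 75% and 33–46% at 83–93%.

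The symmetry argument does not depend on the SD. The percentages rest on the assumed baseline distribution and correlations, which the documents do not give. The documents do not support carrying the point over to the final durability table, the primary ANCOVA, its power or its type I error. It is worth correcting because the rule is plainly unsuitable and the change is small.

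**What to change.** 1. In Protocol 9.5.3.1, delete the sentence that fails a subject for a smaller reduction at Day 35 than at Day 5.
2. In the sentence before it, change NRS to WOMAC. The schedule collects NRS knee pain only at screening and Day 1, so an NRS reduction at Day 5 could not be computed.
3. State in the protocol, or in one line of the SAP, that the SAP 6.3 definition replaces Protocol 9.5.3.1 for all analyses, interim included. It should carry over whole: the 50% threshold on the Study Knee and the allowance of one lapse after Day 5. It should be applied to the visits available at each look. Because SAP 6.3 counts a missing score as non-response at that visit, add that visits not yet due are not counted as missing.

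Interim and final labels can still differ as later visits arrive, but they will then differ because of data and not because of the rule. The cost is a few lines of text, with no new data and no change to the primary analysis.
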